7.11.2 Clinical Laboratory Evaluations

Clinical laboratory variables (including serum gastrin) will be summarized using descriptive statistics for Baseline, postbaseline, and change from Baseline to postbaseline values using the safety analysis set-H for the healing period to summarize changes from Baseline and using the safety analysis set-M for the maintenance period to summarize changes from Week 8.

Individual results for serum fasting gastrin, clinical hematology and chemistry laboratory tests that are within the predefined “markedly abnormal laboratory value (MAV) criteria” will be summarized in tables. All clinical laboratory data will be presented in data listings.

The percentage of subjects with elevated gastrin values ≥ 200 pg/mL and ≥ 400 pg/mL will be summarized.

Elevated hepatic parameters will be summarized.

Summaries and listings of laboratory data will be presented in Systeme Internationale (SI) and conventional units. MAV tables and listings will be presented in the unit specified in the MAV criteria in [Appendix A](#).

7.11.3 Vital Signs

Vital signs will be summarized using descriptive statistics for Baseline, postbaseline, and change from Baseline to postbaseline values using the Safety Analysis Set-H for the Healing Period to summarize changes from Baseline, using the Safety Analysis Set-M for the Maintenance period to summarize changes from Week 8.

All individual vital signs that meet predefined criteria for MAV (Appendix B) will be summarized in tables. All vital sign data will be presented in data listings.

7.11.4 12-Lead ECGs

ECG results will be interpreted using 1 of the following categories: within normal limits, abnormal but not clinically significant, or abnormal and clinically significant. Week 8 Visit ECG assessments will be cross-tabulated against the baseline assessment using the Safety Analysis Set-H. Month 6 ECG assessments will be cross-tabulated against the Week 8 assessment using the Safety Analysis Set-H.

All individual quantitative ECG values that meet predefined criteria for MAV (Appendix C) will be listed.

All ECG data will be presented in a data listing.

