At the Week 8 Visit, all subjects will undergo a physical examination including vital signs, laboratory evaluations, fasting serum gastrin, serum and urine pregnancy test (all women of childbearing potential), ECG and an endoscopy. In addition, study drug will be collected, a review of concomitant medication use will be performed, and an assessment of AEs will be conducted. If the subject's EE has healed completely as determined by endoscopy, the subject will have completed the Healing Period of the study, and will continue in the Maintenance Period. If the subject's EE has not completely healed after 8 weeks of treatment, all Final Visit procedures will be performed and the subject will not be eligible to continue into the Maintenance Period.

For subjects who prematurely discontinue during the Healing Period, efforts should be made to perform all procedures scheduled for the Week 8 / Early Termination Visit no later than 5 days after the last dose of study drug.

At the start of the 6-Month Maintenance Period, subjects with healed EE will be randomized in a 1:1 ratio to one of the following 2 groups; the randomization will be stratified by baseline endoscopic findings (grades A/B or C/D).

- Group I: dexlansoprazole capsules (30 mg QD)
- Group II: placebo (QD)

During the 6-month Maintenance Period, study drug will be self-administered orally, QD in the morning before breakfast. Subjects will continue to document the presence and maximum severity of daytime and nighttime heartburn symptoms using a diary. Subjects will also record the use of rescue medication. Subject visits will be conducted at Months 1, 3 and 6, of the Maintenance Period to collect and/or dispense study drug, assess GERD symptoms, review concomitant medication use, and assess AEs. Endoscopies will be performed at Months 1 and 6/Final Visit to evaluate maintenance of healed EE. Subjects with endoscopic evidence of relapsed EE will be discontinued from the study.

At the Month 1 Visit, the subject will undergo a physical examination including vital signs, laboratory evaluations, endoscopy, and urine pregnancy test (all women of childbearing potential).

[figure not shown]

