7.1.1 Definition of Study Days and Visit Window

Study day will be calculated relative to the date of the first dose of study drug in the study. The study day prior to the first dose of study drug will be calculated as:

$$\text{Date of assessment/event} - \text{date of first dose of study drug.}$$

The study day on or after the first dose of study drug will be calculated as:

$$\text{Date of assessment/event} - \text{date of first dose of study drug} + 1.$$

Baseline is defined as the last non-missing measurement prior to or on Study Day 1 (prior to first dose). The baseline values for the Maintenance Period will be the assessment performed at the Week 8 visit of the Healing Period. The visit windows for each post baseline visit are defined in [Table 7.a](#). If a subject has more than 1 measurement in the same visit window, the measurement closest to the scheduled visit will be used. If 2 measurements in the same window are of equal distance to the scheduled visit, the measurement that occurs after the scheduled visit will be used. If 2 or more measurements occur on the same day, the last value obtained will be used.

Table 7.a Visit Windows for Healing Period

Visit	Scheduled Day	Safety Labs	Serum Gastrin	Vital Signs	ECG	Endoscopy	GERD Symptoms Investigator Assessment
Baseline	Day -1	≤1	≤1	≤1	≤1	≤1	≤1
Week 4	Day 28	2-42	NA	2-42	NA	NA	2-42
Week 8	Day 56	43-70	2-70	43-70	NA	2-70	43-70

Note: Safety labs (including gastrin), vital signs, and ECG data obtained more than 7 days after the last day of study drug and efficacy data obtained more than 7 days after the last day of study drug will not be included in the analyses.

Additionally, for subjects with healed EE by Week 8 who are randomized and receive at least 1 dose of maintenance study drug, the window selection for the Week 8 Visit will include only measurements assessed on or before the date of the first dose of maintenance period study drug; for visits during the Maintenance of Healed EE Period, the window selection will only include measurements assessed after the date of the first dose of maintenance period study drug.

The summary of visits during the maintenance period will be relative to the start of maintenance treatment rather than relative to the start of the study. The table below summarizes the visit windows for each visit during the Maintenance of Healed EE Period.

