For the purpose of the diary compliance calculation and derivation of diary-based endpoints, the last day of study drug in each period will not be included since the subject will not be expected to have completed the diary entries for that day by the Week 8 or month 6 Final Visit. Therefore, summaries for the healing period weeks of treatment will include Study Day 1 through Study Day 70 or the day before the last dose of healing period study drug, or the day before the first dose of maintenance study drug, whichever occurs first; summaries for the Maintenance period will include the day of the first dose of maintenance study drug through maintenance Study Day 180 or the day before the last dose of maintenance study drug, whichever occurs first.

Table 7.b Visit Windows for Maintenance Period

Visit	Scheduled Day	Safety Labs and Vital Signs	Serum Gastrin	ECG	Endoscopy	GERD Symptoms Investigator Assessment
Maintenance Baseline	-1M	≤1M	≤1M	≤1M	≤1M	≤1M
Month 1	30M	2M-60M	2M-60M	NA	2M-60M	2M-60M
Month 3	90M	61M-135M	61M-135M	NA	61M-135M	61M-135M
Month 6	180M	136M-210M	136M-210M	2M-210M	136M-210M	136M-210M

Note: Safety laboratory (including gastrin), vital signs, and ECG data obtained more than 7 days after the last day of study drug of Maintenance period and efficacy data obtained more than 7 days after the last day of study drug of Maintenance period will not be included in the analyses.
 M=Maintenance Period.

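### Two ECG entries in the SAP conflict with the rest of the plan: Table 7.a gives the Week 8 ECG no window, and the Month 6 versus Week 8 table is assigned to Set-H instead of Set-M

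*SAP*

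**What the plan says.** **Schedule.** SAP 4.3 and Protocol 6.1 both list, for all subjects at Week 8, "serum and urine pregnancy test (all women of childbearing potential), ECG and an endoscopy". Protocol 9.3.3.3 and Appendix A also include the Week 8 ECG.

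**Planned tables.** SAP 7.11.4 has two ECG summary tables. The first is "Week 8 Visit ECG assessments will be cross-tabulated against the baseline assessment using the Safety Analysis Set-H". The second is "Month 6 ECG assessments will be cross-tabulated against the Week 8 assessment using the Safety Analysis Set-H". All other ECG output in that section is listings.

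**Windows, Healing Period (SAP Table 7.a).** After the visit name and scheduled day, the columns are safety labs, gastrin, vital signs, ECG, endoscopy and GERD assessment. The rows read "Week 4 Day 28 2-42 NA 2-42 NA NA 2-42" and "Week 8 Day 56 43-70 2-70 43-70 NA 2-70 43-70".

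**Windows, Maintenance Period (SAP Table 7.b).** After the visit name and scheduled day, the columns are safety labs with vital signs, gastrin, ECG, endoscopy and GERD assessment. The rows that matter are "Maintenance Baseline -1M ≤1M ≤1M ≤1M ≤1M ≤1M" and "Month 6 180M 136M-210M 136M-210M 2M-210M 136M-210M 136M-210M". SAP 7.1.1 adds: "The baseline values for the Maintenance Period will be the assessment performed at the Week 8 visit of the Healing Period".

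**Analysis sets.** SAP 7.11 assigns maintenance-period safety analyses to Set-M, by treatment group. SAP 7.11.2 (laboratory) and 7.11.3 (vital signs) use Set-M for change from Week 8. Protocol 13.1.4 asks for ECG summaries separately for each period and by double-blind treatment group.

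**The concern.** The healing ECG table depends on a Week 8 record, but the visit-window table says no such window applies. SAP 7.1.1 chooses among several measurements by closeness to the scheduled visit within a window. Without a window that rule cannot operate. Subjects who are not healed, or who stop early, are in Set-H and so belong in this table, yet the SAP does not say how to choose among a final, early-termination, repeat or unscheduled ECG.

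The Month 6 table is the only maintenance-period ECG summary and therefore the only tabulated ECG comparison against placebo. Set-H is defined by dosing in the Healing Period, and its natural treatment groups are dexlansoprazole 60 mg and lansoprazole 30 mg. Tabulated that way, each column would pool subjects re-randomized to dexlansoprazole 30 mg with subjects re-randomized to placebo, and the placebo-controlled display would be lost.

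**Working it through.** No sample-size or power figure is involved, so this is a cross-check of text and tables followed by simple counts.

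**1. Is the NA really under ECG?** Table 7.a has 8 headers, and the Week 8 row has 8 cells, so they align one to one:

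| Column | Week 4 | Week 8 |
|---|---|---|
| Safety labs | 2-42 | 43-70 |
| Serum gastrin | NA | 2-70 |
| Vital signs | 2-42 | 43-70 |
| ECG | NA | NA |
| Endoscopy | NA | 2-70 |
| GERD assessment | 2-42 | 43-70 |

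The Healing Period therefore has no post-baseline ECG window. Gastrin and endoscopy are also measured at Week 8 but not at Week 4, and both have 2-70. The note under Table 7.a excludes ECGs taken more than 7 days after the last day of study drug. That presupposes that post-baseline ECGs enter the analysis.

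**2. Whom does the gap affect?** For subjects who enter Maintenance, the Maintenance Baseline ECG window in Table 7.b (≤1M), read with the rule that maintenance baseline is the Week 8 assessment, identifies the record. The gap is mainly for the others:

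- From planned entry (SAP 6.0): 450 − 300 = 150, and 150/450 = 33.3%.
- If every healed subject entered and 85% applied to all randomized: 450 − 0.85 × 450 = 450 − 382.5 = 67.5, about 68 (15.0%).
- If every healed subject entered and 85% applied to completers after 10% dropout: 450 − 0.85 × 0.90 × 450 = 450 − 344.25 = 105.75, about 106 (23.5%).

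For example, a subject who stops early and has the final-visit ECG on Day 20, within 7 days of the last dose, passes the exclusion rule but falls in no ECG window.

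**3. What does Set-H do to the Month 6 table?** Everyone in Set-M was dosed in the Healing Period, so Set-M lies within Set-H. There are two cases:

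- *Columns by maintenance arm, subjects with both ECGs:* the same subjects and the same counts under either set.
- *Columns by healing arm:* with equal entry from both arms, 300 / 2 = 150 entrants per column. With 1:1 re-randomization, 150 / 2 = 75 on dexlansoprazole 30 mg and 75 on placebo in each column.

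**4. Related protocol lists.** Protocol 9.3.5 (final visit) and 9.3.6 (unscheduled visit) do not list an ECG. Protocol 6.1 requires one at Month 6, and Appendix A marks one at both visits.

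**The case against.** **The 33% overstates the window problem.** Appendix A schedules only one post-baseline healing ECG, and early discontinuers undergo the Week 8/Final Visit procedures. Most non-entrants will have one unambiguous ECG or none. A real choice arises only with a repeat or unscheduled ECG, and the documents give no number for those. This stands: 150 is the size of the group without a window and at most an upper bound on ambiguous records. The contradiction between Table 7.a and SAP 7.11.4 remains.

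**A selection rule exists.** The 7-day exclusion and the tie-breaks in SAP 7.1.1 are written down. That is true, but the tie-breaks work only inside a window, and the ECG has none.

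**The Set-H harm is unlikely.** SAP 7.11 and Protocol 13.1.4 already point to Set-M and to maintenance treatment groups, so a sensible programmer would show the table that way. This largely stands and is why the effect is given as conditional. But the specific sentence in 7.11.4 contradicts the general rule, and nothing says which governs.

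**The protocol lists are a side issue.** The list in 9.3.6 is a minimum list, and Appendix A governs the schedule. This is accepted; the lists are only a consistency point.

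**The window 2-70 is not dictated by the text.** The same row also uses 43-70, and 2-70 would let a very early ECG carry the Week 8 label. That trade-off is real and is taken up in the fix.

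**Conclusion.** Both SAP entries are wrong as written, and the point is minor. The Week 8 ECG is scheduled and tabulated but has no window. This mainly concerns about 150 of 450 planned subjects (33%), or 68 to 106 (15% to 24%) if all subjects healed at the assumed 85% rate enter Maintenance. These are group sizes, and the number of records actually in doubt is likely to be smaller.

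The Set-H assignment contradicts SAP 7.11, the parallel rules in 7.11.2 and 7.11.3, and Protocol 13.1.4. Its effect ranges from none (maintenance-arm columns, subjects with both ECGs) to loss of the placebo-controlled display (healing-arm columns, about 75 and 75 per column, assuming equal entry from both healing arms).

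Only two descriptive safety tables are affected. The ECG listings, the listing of markedly abnormal values, and all efficacy results, alpha and power are untouched.

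**What to change.** - **SAP Table 7.a:** replace NA for the Week 8 ECG with a window. The best fit is 2-70: it matches gastrin and endoscopy in the same row and parallels the 2M-210M ECG window in Table 7.b. With 43-70, an ECG on Days 2-42 would belong to no visit, because the Week 4 ECG cell is also NA. The price of 2-70 is that an early-termination ECG can be labelled Week 8, as already happens for endoscopy.
- **SAP 7.11.4:** change Set-H to Set-M for the Month 6 versus Week 8 table. State that it is shown by maintenance treatment group (dexlansoprazole 30 mg, placebo) among subjects with both ECGs.
- **Protocol 9.3.5 and 9.3.6:** reconcile the procedure lists with Section 6.1 and Appendix A.

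The cost is two SAP entries and two protocol lists. No new data are needed.

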9.1.13 ECG Procedure

A standard 12-lead ECG will be recorded. The investigator (or a qualified observer at the investigational site) will interpret the ECG using 1 of the following categories: within normal limits, abnormal but not clinically significant, or abnormal and clinically significant.

The time that the ECG was performed will be recorded. The following parameters will be recorded on the eCRF from the subject's ECG tracing: heart rate, RR interval, PR interval, QT interval, and QRS interval.

As ECG tracings on thermal paper fade over time, any such tracings should be completely photocopied and both the original tracing and the counter-signed copy should be filed in the subject's medical record.

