13.1.4 Safety Analysis

Safety will be assessed by summarizing the incidence of AEs, clinical laboratory values, gastrin levels, ECG, and vital signs.

Summary of AEs, ECG results, clinical laboratory values, gastrin levels, and vital signs will be provided separately for the Healing Period and for the Maintenance Period. For the Healing Period, baseline values will be the last available assessment before the first dose of study drug. The baseline values for the Maintenance Period will be the assessment performed at the Week 8 visit of the Healing Period.

All AEs will be coded using MedDRA. Treatment-emergent adverse events (TEAE) will be summarized using preferred term and primary system organ class overall, by severity, and by relationship to study drug for each treatment group. Separate summaries will also be generated for treatment-related adverse events (TRAEs) overall and by severity. AEs that were reported more than once by a subject during the same period will be counted only once for that subject and period at the maximum severity.

Other safety assessments (ECG results, clinical laboratory values, gastrin levels, and vital signs) will be summarized by double-blind treatment group at all visits assessed using descriptive statistics. Values outside the reference ranges and markedly abnormal laboratory values will be flagged and tabulated.

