7.11 Safety Analysis

All safety analyses will be performed using the Safety Analysis Set-H for the Healing Period, and using the Safety Analysis Set-M for the maintenance period. Results will be summarized by treatment group.

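### SAP 7.11.4 plans shift tables and listings for ECG but no by-arm descriptive statistics for the measured intervals, an unrecorded departure from Protocol 13.1.4

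*SAP*

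**What the plan says.** **Protocol.** Section 13.1.4 treats ECG together with laboratory values, gastrin and vital signs: "Other safety assessments (ECG results, clinical laboratory values, gastrin levels, and vital signs) will be summarized by double-blind treatment group", at all visits assessed and with descriptive statistics. Section 9.1.13 has the site record "heart rate, RR interval, PR interval, QT interval, and QRS interval" on the eCRF, alongside a three-category interpretation. Appendix A schedules ECGs at Screening, Week 8 and Month 6.

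**SAP.** Section 7.11.4 plans three things for ECG:

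- Shift tables of the three-category interpretation. At Week 8: "Week 8 Visit ECG assessments will be cross-tabulated against the baseline assessment using the Safety Analysis Set-H". At Month 6: "Month 6 ECG assessments will be cross-tabulated against the Week 8 assessment using the Safety Analysis Set-H". Under the general rule of SAP 7.11 ("Results will be summarized by treatment group") these are by arm.
- A listing of outlying measurements: "All individual quantitative ECG values that meet predefined criteria for MAV (Appendix C) will be listed".
- A complete listing: "All ECG data will be presented in a data listing".

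SAP 7.11.2 and 7.11.3, by contrast, give laboratory values and vital signs descriptive statistics at baseline and postbaseline, change from baseline, and tables of markedly abnormal values. SAP Appendix C sets ECG limits for heart rate, QT, QTcB and QTcF only. SAP 7.13 reports no changes.

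**The concern.** The Protocol places ECG results in the same sentence as laboratory values and vital signs and promises the same kind of summary for all of them. The SAP keeps that promise for the others but not for the ECG measurements, and gives no reason. A programmer who follows SAP 7.11.4 would produce no table containing a mean QT, QTc, PR, QRS or RR.

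ECG is a stated safety assessment in both periods. A modest average shift in an interval between dexlansoprazole and lansoprazole, or between dexlansoprazole and placebo, is what a table of means and changes would show. A three-category reading and a list of extreme values are poorly suited to showing it. PR, QRS and RR are the least covered, with neither a summary nor an Appendix C limit.

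**Working it through.** **1. Text comparison.** The point rests on no sample-size or power statement, so there is no figure in the plan to reproduce. What is planned for each item in the SAP:

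| Item | By-arm descriptive statistics and change | Markedly abnormal values | Full listing |
|---|---|---|---|
| Laboratory values, gastrin (7.11.2) | yes | tabulated | yes |
| Vital signs, including pulse (7.11.3) | yes | tabulated | yes |
| ECG interpretation, 3 categories (7.11.4) | shift tables | not applicable | yes |
| ECG heart rate, QT, QTcB, QTcF (7.11.4, App. C) | none named | listed only | yes |
| ECG PR, QRS, RR (7.11.4, App. C) | none named | no criterion | yes |

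Protocol 13.1.4 asks that ECG results "will be summarized by double-blind treatment group at all visits assessed using descriptive statistics". The third row meets part of that. The last two rows do not meet it.

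**2. Does another SAP rule fill the gap?** SAP 7.1 says how continuous data are to be summarized (number of subjects, mean, standard deviation, median, minimum, maximum). It fixes a format and does not say which variables get a table. SAP 7.11.2 and 7.11.3 state descriptive statistics explicitly for their variables, whereas 7.11.4 specifies listings for the measurements. The general rule therefore does not restore the tables.

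**3. Illustrative precision of the missing table.** The documents give no ECG standard deviation, so the SD of QTc change is assumed to be 15 to 20 msec. Numbers per arm follow from the sample-size section (Protocol 13.2, SAP 6.0):

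- Healing: 225 × (1 − 0.10) = 202.5, taken as 202.
- Maintenance: 150 × (1 − 0.33) = 100.5, taken as 100.

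The 95% half-width of the between-arm difference in mean change is 1.96 × SD × √(2/n):

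- Healing, SD 15: 1.96 × 15 × √(2/202) = 2.9 msec. SD 20: 3.9 msec.
- Maintenance, SD 15: 1.96 × 15 × √(2/100) = 4.2 msec. SD 20: 5.5 msec.

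**4. Illustrative behaviour of the outlier listing.** The Appendix C QTc rule (at least 500 msec, or a rise of at least 30 msec together with a value of at least 450 msec) was simulated under further assumptions: mean baseline QTc of 400 to 420 msec, SD 20 msec at each visit, and SD of change 15 to 20 msec. The expected number flagged per 202 subjects is 0.2 to 3.7 with no shift and 0.6 to 7.1 with a true 5-msec mean shift. The two ranges overlap heavily, so the length of such a listing says little about a mean shift of that size.

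**The case against.** **The SAP does more than list outliers.** A reader might infer that outliers are all the SAP reports and that an average ECG shift cannot be seen. The documents do not support that. SAP 7.11.4 also has by-arm shift tables and a listing of every ECG value, from which means could be derived. What is missing is a planned table; the data are still there. This objection stands and limits the point.

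**Heart rate is mostly covered.** Protocol 9.1.5 collects pulse as a vital sign, and SAP 7.11.3 gives vital signs descriptive statistics and change by arm. An average rate shift would be visible there. This also stands, and leaves QT/QTc, PR, QRS and RR.

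**The Protocol wording is general.** Protocol 13.1.4 says ECG results and names no interval. SAP 7.11.4 uses the same term for the categorical reading, and Protocol 13.1 leaves further methodological detail to the SAP. Shift tables therefore meet part of the commitment. They do not account for the five measurements that Protocol 9.1.13 collects, and leaving out a planned type of summary goes beyond adding detail.

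**QT has been studied before.** Protocol 4.1 reports no QT prolongation at doses up to 300 mg, five times the highest dose here (300 / 60 = 5). That lowers the importance of the point. It does not explain an unrecorded departure, it does not address PR or QRS, and Protocol 4.2 describes this as the first study of the capsules in Chinese subjects with EE.

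**The numbers are assumed.** No ECG mean, SD or correlation is given, and the trial has no ECG power objective. A reader might take the Healing Period precision to apply to the placebo comparison too. It does not, because the plan's own 33% dropout leaves about 100 per arm.

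**Conclusion.** The point holds as a minor misalignment between Protocol and SAP. SAP 7.11.4 contains no by-arm descriptive statistics for quantitative ECG parameters, Protocol 13.1.4 plans descriptive statistics for ECG results by arm at all visits, and SAP 7.13 does not record the difference. This conclusion rests on the text alone.

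In practice, a mean shift in QT/QTc, PR, QRS or RR would be in no planned summary, although it could be recovered from the full listing. The precision and flag-count figures are illustrations that depend wholly on the assumed QTc mean and SDs, and nothing in the conclusion turns on them. No primary or secondary efficacy conclusion is affected.

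**What to change.** Add to SAP 7.11.4, by treatment group, n, mean, SD, median, minimum and maximum of the value and of the change for heart rate, RR, PR, QRS, QT and the derived QTcB and QTcF:

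- at Week 8, change from baseline, on Safety Set-H;
- at Month 6, change from Week 8, on Safety Set-M.

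Also give the number and percentage of subjects meeting the Appendix C criteria by arm. Protocol 13.1.4 does not require this for ECG, but it would match how the SAP treats laboratory values and vital signs. If the sponsor prefers not to produce these tables, SAP 7.13 should record the departure from Protocol 13.1.4 with a reason.

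Two related items should be settled in the same edit. SAP Table 7.a gives no Week 8 ECG window (it shows NA), although a Week 8 ECG is scheduled and tabulated. The Month 6 shift table names Safety Set-H, while SAP 7.11 assigns maintenance safety analyses to Set-M.

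The cost is SAP wording and a few standard tables per period. The measurements are already on the eCRF, so no new data are needed.
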